8.0 RESEARCH QUESTION AND OBJECTIVES

The objective of the Menveo Pregnancy Registry is to evaluate pregnancy outcomes among women immunized with the Menveo vaccine within 28 days prior to conception or at any time during pregnancy. The primary outcomes of interest include major congenital malformations (MCM), preterm birth, and low birth weight (LBW).

Other pregnancy outcomes will be collected, including stillbirths and SABs. The probability of SAB varies greatly as a function of when the pregnancy is enrolled in the registry ([Savitz, 2002](#)). Because pregnancies will be reported to the registry at different and imprecise times during gestation, calculation of the prevalence rate of SAB from the registry is deemed inappropriate and could lead to erroneous conclusions. For example, if a woman enrolls in the registry at 16 weeks of pregnancy, only an SAB after this time could be detected and included in prospective reports. Similarly, SABs occurring earlier in gestation may not have been recognized and/or reported.

This registry is primarily descriptive and designed to detect potential safety signals rather than test hypotheses.

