9.2.3 Study Population Selection

The minimum criteria required for enrollment into the registry are as follows:

- Sufficient evidence to confirm that Menveo exposure occurred within 28 days prior to conception or at any time during pregnancy

- Sufficient information to determine whether the pregnancy is prospectively or retrospectively registered (ie, whether the outcome of pregnancy was known at the time of first contact with the registry)
- Date the pregnancy exposure is registered
- Full reporter (ie, HCP) contact information to allow for follow-up (name, address, etc.)

Because registry enrollment is open to all eligible pregnant women, an active recruitment campaign will reach out to immunization providers and their patients in a broad variety of settings. The recruitment strategy will target HCPs who are known to immunize patients specifically with the Menvo vaccine. These providers will be identified through NVD Menvo distribution data and medical science liaisons (MSLs), as well as HCP provider networks and health maintenance organizations (HMOs).

This targeted awareness will include the distribution of a comprehensive informational kit designed to solicit interest among pregnant women in registry participation. All messaging will be in line with product labeling.

The kit may include:

- Branded registry information sheet and/or brochure that will briefly describe the registry purpose and procedures
- Enrollment form and sample patient consent form
- Prescribing information
- Participant consent to contact card (this card enables the RCC to contact the potential patient and provide additional information about the registry)

Persistent awareness activities incorporating the above awareness materials as well as a variety of other approaches such as internet, product labeling, and messaging by MSLs may also be used, including the following:

- Internet:
 - FDA listing of pregnancy registries on www.fda.gov
 - www.clinicaltrials.gov
 - Society for Maternal-Fetal Medicine listing of registries
 - PPD website
 - NVD website
- Print:
 - Menvo prescribing information

- Menveo medication guide
- Medical journal advertising and/or direct to physician advertising
- Registry contact information in report(s)
- Education:
 - MSL outreach to treating HCPs
 - Scientific presentations and publications
 - Distribution of report(s) to HCPs

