Maternal Information

- Maternal demographics (age, ethnicity, race)
- LMP
- EDD determined from LMP
- CEDD (e.g., by ultrasound), if available
- Prenatal tests (diagnostic or screening) performed, date of test, and findings including the identification of congenital anomalies

Maternal Obstetrical History

- Number of previous pregnancies
- Outcome of previous pregnancies: live births, stillbirths, SABs, IABs, ectopic pregnancies, molar pregnancies
- History of offspring with congenital anomalies
- Maternal and paternal history of congenital anomalies

Maternal Menveo Exposure (may be provided initially by the pregnant woman at registry enrollment and confirmed by the vaccinating HCP)

- Menveo administration, including dose, timing, and lot number

Other Conditions and Exposures

- Concurrent maternal conditions
- Concomitant medications taken during pregnancy
- Tobacco, alcohol, and illicit drug use during pregnancy

Pregnancy Follow-up

Around the end of the second trimester and in the month of the EDD, the ***Interim Pregnancy Follow-up Form*** and ***Pregnancy Outcome Form*** (respectively) will be requested from the obstetric HCP.

Information Collected at Interim Pregnancy Follow-up and Pregnancy Outcome

Follow-up at End of Second Trimester

Pregnancy Status

- Updates to EDD (ie, CEDD)
- Subsequent prenatal tests (diagnostic or screening) performed and findings including the identification of congenital anomalies
- Pregnancy complications (preterm labor, eclampsia, placental abruption)
- Details of pregnancy outcome if pregnancy is not ongoing as described below

Other Exposures

- Concomitant medications
- Tobacco, alcohol, and illicit drug use during pregnancy

Additional Information Collected at Pregnancy Outcome

Fetal Outcome

- Pregnancy outcome (live birth, stillbirth, SAB, IAB, ectopic pregnancy, molar pregnancy)
- Date of outcome of pregnancy
- Gestational age at outcome
- Fetal/infant characteristics: sex, birth weight
 - MCM(s) and assessment of potential contributing factors
 - For a fetal loss (SAB, stillbirth), factors that may have had an impact on the fetal loss and attribution

Targeted Follow-up Process

If there is an MCM or other event of interest noted, in order to properly characterize the event, additional information may be requested from the reporting HCP on the ***Targeted Follow-up Form***:

- Details of the MCM/condition
- Etiology
- Outcome attribution
- Specific questions requested by NVD and/or the MCM evaluator

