9.5 Study Size

Currently the market share of Menveo is approximately 20%, with an annual absolute dose distribution of 1.8 million in 2012. It can be assumed that market shares will remain stable over the course of the 3-year duration of the study. The Advisory Committee on Immunization Practices (ACIP) recommends routine administration of a MenACWY vaccine for all persons aged 11 through 18 years. A single dose of vaccine should be administered at age 11 or 12 years, and a booster dose should be administered at age 16 years. It is roughly estimated that of all Menveo vaccinations, approximately 76% are provided to individuals less than 18 years of age ([Novartis Vaccines and Diagnostics, 2012](#)). Given the low rate of pregnancy in this age group, exposure during pregnancy at the recommended ages can be expected to occur infrequently. Likewise, vaccination among women of peak reproductive age (25-29 years) can also be expected to be rare ([Ventura, 2012](#)). In addition, willingness to participate and completion of follow-up in the pregnant adolescent population are expected to be very low. It is therefore anticipated that, per year, approximately 15 exposed women will be enrolled through the registry system and that approximately 60 supplemental identified exposures of Menveo in pregnancy can be expected from external sources.

The registry is expected to prospectively enroll approximately 100 women with exposure to Menveo 28 days prior to conception or during pregnancy over a 3-year period. Approximately 58% of these pregnancies can be expected to result in a live birth ([Ventura, 2012](#)). Given the patient population will be mainly adolescents, a high percentage of these pregnancies can be expected to be unintended, unwanted, and likely

to result in IAB. Therefore, it is anticipated that the registry will yield approximately 58 live births. It is expected that the vast majority (99%) of pregnancy exposures will occur within 28 days prior to conception or early in the first trimester (before pregnancy status is known). If exposures occur later in pregnancy, results will be stratified by trimester of exposure, acknowledging that the power of stratified analyses to detect statistically significant differences will be limited by the sample size of each subgroup.

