The expected low frequency of Menveo exposure in pregnancy will limit the statistical power of this study. As noted below, there should be sufficient power to identify risks for relatively common outcomes such as preterm birth and LBW. However, there is less power to identify risks of rarer outcomes such as MCM.

According to the CDC MACDP, the prevalence rate of MCMs for mothers <25 years of age in the US is 2.54% ([Correa, 2007](#)). With a sample size of 58 first trimester exposed pregnancies resulting in a live birth, the study will have 80% power to detect a 4.46-fold increase in the prevalence rate of MCMs as compared with the CDC MACDP rate.

According to the CDC National Vital Statistics System (NVSS), the prevalence rate of preterm birth for mothers <25 years of age is 12.37% ([Martin, 2012](#)). With a sample size of approximately 58 exposed live births, the study will provide 80% power to detect a statistically significant 1.99-fold increase in the prevalence rate of preterm birth as compared with the CDC NVSS rate.

According to the CDC NVSS, the prevalence rate of LBW for mothers <25 years of age is 8.70% ([Martin, 2012](#)). With a sample size of 58 exposed live births, the study will provide 80% power to detect a statistically significant 2.40-fold increase in the prevalence rate of LBW as compared with the CDC NVSS rate.

The registry acknowledges the challenges of enrolling this number of exposed pregnancies and will carefully monitor enrollment trends and outcomes. This is an open registry with initiation of patient recruitment from the time of launch.

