9.7 Data Analysis

Registry Case Management and Disposition

Prospective Registry Reports

The registry will encourage prospective registration, which is defined as registration of a pregnancy exposure prior to knowledge or perceived knowledge of the pregnancy outcome (e.g., structural defect or genetic abnormality noted on a prenatal test). Those with no abnormalities identified on a prenatal test prior to enrollment will be considered prospective and included in the analysis. The rationale, potential bias, and analytic techniques to address any bias that may be introduced by this practice are addressed in [Section 9.7.4](#).

Data from HCP provider networks and HMOs that provide de-identified data on all exposed pregnancies in their network will fall into the category of prospective registry reports, as these networks/HMOs provide objective data on every pregnancy exposure in the network/HMO, both positive and negative outcomes. Thus, they avoid the reporting bias inherent in retrospective reporting only after a negative outcome has been noted.

Retrospective Registry Reports

Retrospective reports will also include subjects for whom the pregnancy outcome has already occurred or an abnormality has been identified on a diagnostic or screening prenatal test prior to enrollment. Retrospective reports can be biased toward the reporting of more unusual and severe cases and are less likely to be representative of the general population experience than reports reported prior to knowledge of outcome. Therefore, retrospective reports will not be included in the primary analysis and statistical calculation of risk. Retrospective reports with reported MCMs and/or spontaneous fetal losses will be reviewed to aid in detection of early signals and listed in registry reports. Retrospective reports will not be actively solicited by the registry and will not be captured in the registry database unless a congenital anomaly is reported.

Loss to Follow-Up

For a prospective report or pregnancy where follow-up information on the pregnancy outcome (live birth, fetal loss, etc.) is never obtained or is unavailable, the pregnancy will be considered lost to follow-up. Subjects lost prior to pregnancy outcome will be tallied in the registry reports but not included in the statistical analyses.

Duplicate Registry Reports

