9.7.3 Statistical Methods

Overall and stratum-specific point estimates and 1-sided 95% confidence intervals will be calculated using the exact binomial distribution for prevalence rates of MCMs, preterm birth, and LBW among pregnant women exposed to Menveo and their live births. Most structural defects have their origins in the first trimester of pregnancy, the period of organogenesis. In addition to overall prevalence of MCM, the analysis of MCMs will be stratified by trimester of exposure to Menveo. The prevalence rate of combined MCMs reported to the registry will be calculated as a proportion with the number of MCMs as the numerator and the number of live births as the denominator, among women with first trimester exposure. Pregnancy losses with reported MCMs occurring at or after 20 weeks' gestation will be included in the numerator of the estimate of risk for MCMs to increase sensitivity and to allow comparison of outcomes with the CDC MACDP, which calculates rates by this convention. A secondary analysis will be conducted including pregnancy losses with reported MCMs occurring at less than 20 weeks' gestation in the calculation of risk. The prevalence rate of combined MCMs in exposed cases will be compared with that of the CDC MACDP ([Correa, 2007](#)).

Only cases meeting the CDC MACDP criteria for a defect or with 2 or more conditional defects will be included in the primary analysis. Single minor defects do not constitute a MCM according to the CDC MACDP classification; therefore, they will be listed in the report, but not included in the primary analysis.

The prevalence rate of preterm births and LBW will be calculated as proportions, with the number of live births as the denominator. These prevalence rates in exposed cases will be compared with those of the CDC NVSS ([Martin, 2012](#)). Because MCMs are often associated with preterm birth and LBW, infants with MCMs will be excluded from

analyses of these outcomes and will not be counted in the numerator or denominator when prevalence rates are determined.

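### Preterm birth is counted over all live births, so women who register at or after 37 weeks are guaranteed non-cases in the denominator and pull the rate below its NVSS comparator

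*Protocol*

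**What the plan says.** Section 9.3.2 defines preterm birth as birth before 37 weeks and lists it among the primary outcomes' definitions. On the analysis, Section 9.7.3 says: "The prevalence rate of preterm births and LBW will be calculated as proportions, with the number of live births as the denominator". It removes infants with MCMs from numerator and denominator and compares the result with NVSS.

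Entry is governed by two sections. Section 9.2.3 requires enough information to tell "whether the outcome of pregnancy was known at the time of first contact with the registry". Section 9.7 defines a prospective report as "registration of a pregnancy exposure prior to knowledge or perceived knowledge of the pregnancy outcome". Neither sets a latest gestational age. Reports made after the outcome are retrospective and are left out of the risk calculation. Networks and HMOs are treated as prospective because "these networks/HMOs provide objective data on every pregnancy exposure in the network/HMO, both positive and negative outcomes".

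Section 8.0 recognises late entry for spontaneous abortion (SAB): "Because pregnancies will be reported to the registry at different and imprecise times during gestation, calculation of the prevalence rate of SAB" is judged inappropriate. Section 9.7.3 mentions gestational age at enrollment only as a possible subgroup variable. Section 9.5 says of the planned size that "there should be sufficient power to identify risks for relatively common outcomes such as preterm birth and LBW".

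**The concern.** A woman still pregnant at 37 weeks or later when she registers has zero probability of a preterm birth. Her infant adds one to the denominator and nothing to the numerator. The women who would balance her, those who delivered before 37 weeks without having registered, can only enter as retrospective reports and are excluded. NVSS counts all births and has no such selection, so the two rates are not on the same footing.

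The mechanism acts in one direction: it makes the registry rate look lower than it should. In a registry that looks for increases in a primary outcome, that is the less safe direction. The possible subgroup by gestational age at enrollment might reveal the problem, but it would leave the overall rate and its NVSS comparison as they are. The confidence interval does not reflect this bias either.

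**Working it through.** **Inputs from the protocol**
- Reference preterm rate p0 = 12.37%, live births n = 58, stated 80% power at a 1.99-fold increase (Section 9.5).
- One-sample binomial, 1-sided 5% (Section 9.6.2).
- Sources: per year, "approximately 15 exposed women will be enrolled through the registry system and that approximately 60 supplemental identified exposures of Menveo in pregnancy" (Section 9.5). Over 3 years, direct enrollees number 3 × 15 = 45. If the 60 external exposures are a total, direct enrollees are 45 of 105, close to the target of 100. If they are per year, direct enrollees are 45 of 45 + 180 = 225.

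**Assumptions**
- 10–30% of direct enrollees register at or after 37 weeks. The protocol gives no figure.
- Complete network/HMO cohorts are unaffected.
- The yield of live births is the same for both sources.

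**Step 1: the plan's own figure.** The smallest count r with P(X ≥ r | 58, 0.1237) ≤ 0.05 is r = 12 (exact alpha 0.0494). At 0.1237 × 1.99 = 0.2462, power is 0.799. The stated 80% reproduces. The count of 12 is inferred from this calculation; the protocol does not state it as a signal rule.

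**Step 2: effect of late entrants left in.** If a share s of live births comes from women registered at or after 37 weeks, the expected proportion is p × (1 − s). Here s = (direct share) × (late share among direct enrollees).

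| Direct share | Late among direct | s | Late births of 58 | Expected rate, no vaccine effect | Power at 1.99-fold | Fold for 80% power |
|---|---|---|---|---|---|---|
| 45/105 | 10% | 4.3% | 2.5 | 11.84% | 74.3% | 2.08 |
| 45/105 | 20% | 8.6% | 5.0 | 11.31% | 67.9% | 2.18 |
| 45/105 | 30% | 12.9% | 7.5 | 10.78% | 60.7% | 2.28 |
| 45/225 | 10% | 2.0% | 1.2 | 12.12% | 77.4% | 2.03 |
| 45/225 | 20% | 4.0% | 2.3 | 11.88% | 74.7% | 2.07 |
| 45/225 | 30% | 6.0% | 3.5 | 11.63% | 71.9% | 2.12 |

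The downward shift, p0 × s, runs from 0.2 to 1.6 percentage points. The binomial standard error is √(0.1237 × 0.8763 / 58) = 0.043, or 4.3 points.

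**Step 3: what restriction does.** Leaving out women registered at or after 37 weeks removes this part of the bias: their share becomes zero and the expected rate returns to 12.37%. It does not restore power, because these women carry no information on preterm birth either way. At s = 8.6%, power is 0.679 crude and 0.681 restricted (n = 53). The critical count stays at 12 for every n from 52 to 58. At s = 5% and 10% the detectable increase is about 2.10- and 2.21-fold under both analyses. At n = 51 the critical count drops to 11 and power is 0.743; that step comes from the discreteness of the exact test and is not a benefit of the restriction.

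**The case against.** The strongest reply is that the effect may be negligible. The late-entry share is assumed. Section 9.5 expects 99% of exposures within 28 days before conception or early in the first trimester, recruitment works through vaccinating providers, and the schedule places a follow-up at about 24 weeks after enrollment. All of this favours early entry, so a near-zero share is possible. The upper end of the range also requires reading the 60 external exposures as a total, although the sentence opens with a per-year figure. On the per-year reading the shift is 0.25–0.74 points. Up to six late entrants could be removed without moving the critical count. The registry is descriptive (Section 9.7.1), Section 9.9 already allows for selection in either direction, and subgroup detail is deferred to the SAP. Finally, preterm risk falls late in pregnancy, so late entry hides less of it than it hides of SAB.

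Most of this stands as a limit on size. The effect is probably modest, the power figures are secondary, and the net difference from NVSS cannot be signed. It does not answer the point itself. The protocol fixes the denominator, so the matter is not simply left open for the SAP, and an optional subgroup does not alter the overall rate. The SAB analogy need not be exact: for a woman registering at or after 37 weeks, the whole preterm risk period has passed.

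**Conclusion.** The concern holds and should be fixed. As written, the preterm proportion includes births that cannot be cases, and the expected rate falls below the NVSS rate for any share of late direct entrants above zero. On the assumed 10–30% late entry among direct enrollees, the rate expected with no vaccine effect is 11.8–10.8% (45 of 105 direct) or 12.1–11.6% (45 of 225 direct), against 12.37%. The true share is unknown. Entry between 20 and 37 weeks adds some truncation in the same direction that these figures do not count. The conclusion concerns this mechanism only; other selection may offset or add to it.

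**What to change.** In Section 9.7.3, for the NVSS comparison of preterm birth:

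- Restrict the denominator to live births without MCMs from pregnancies registered before 37 completed weeks. Date registration with the rule already in that section: most reliable EDD, or CEDD where given, and LMP if there is no EDD.
- Keep in full the network/HMO cohorts that report every exposed pregnancy.
- Keep the exact binomial method.
- Report the crude proportion over all live births without MCMs alongside, with the number registered at or after 37 weeks.
- Add a delayed-entry (left-truncated) estimate as a sensitivity analysis for entry between 20 and 37 weeks. It will rest on small early risk sets and should stay a sensitivity analysis.

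The cost is wording in Section 9.7.3 and the SAP. Registration date is a minimum criterion in Section 9.2.3, and Section 9.4 already collects LMP, "EDD determined from LMP" and CEDD. The statistical price is a smaller denominator and a wider interval. With 7 cases, for example, the estimate and 1-sided 95% exact upper bound are 12.1% and 21.5% at n = 58, 12.7% and 22.6% at n = 55, and 13.7% and 24.2% at n = 51. The gain is a less biased estimate, not more power.

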
For MCM, the overall prevalence of MCM will be reported. Since most structural defects have their origins in the first trimester of pregnancy during the period of organogenesis, analyses of MCM will be stratified by trimester of exposure if applicable. It is expected that the vast majority (99%) of prenatal exposures will occur during the first trimester before the pregnancy is recognized. The prevalence rate of combined MCMs reported to the registry will be calculated as a proportion, with the number of MCMs as the numerator and the number of live births as the denominator. Pregnancy losses with reported MCMs occurring at or after 20 weeks' gestation will be included in the numerator of the estimate of risk for MCMs to increase sensitivity and to allow comparison with the CDC MACDP following the outcome, which calculates rates by this convention. A secondary analysis will be conducted including pregnancy losses with reported MCMs occurring at less than 20 weeks' gestation in the calculation of risk. The prevalence rate of combined MCMs in exposed subjects will be compared with that of the CDC MACDP (Correa, 2007). The prevalence rates of preterm births and LBW will be calculated as proportions, with the number of live births as the denominator. These prevalence rates in exposed subjects will be compared with those of the CDC NVSS (Martin, 2012).
			

Informed Consent and Ethical Approval: As a post marketing safety reporting activity, this registry qualifies for exemption of US Health Insurance Portability and Accountability Act (HIPAA) authorization. It also qualifies for a waiver of documentation of informed consent (verbal consent) for adult women who self-enroll, and it qualifies for a waiver of informed consent for de-identified data reported to the registry. If a minor requests participation in the registry and all eligibility criteria are met, the registry will obtain assent from the minor and signed written consent from the parent or guardian. The protocol and informed consent waivers will be submitted to an IRB for approval prior to registry implementation.
			

Milestones:
 
Start of data collection: The registry will be implemented after approval by applicable regulatory authority and central IRB. Data collection will commence after a start-up period of approximately 4 months.
			

Name of Sponsor	Protocol number:	Health authority study registration number(s):	Date of Protocol Abstract:

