9.2.3.1 Reference Groups

Given the inherent difficulties in identifying a comparison group (Covington, 2009), several different methods may be used to review the data for safety signals. As described below, background rates from external surveillance sources and rates from published literature will be the primary comparators. To the extent possible, comparator rates will be age-adjusted to reflect the age distribution of the Menveo Pregnancy Registry population.

Background Rates on Pregnancy Outcomes

Background rates in the general population on pregnancy outcomes, such as premature birth and LBW, are readily available from national vital statistics or publications in the scientific literature (Martin, 2012).

Background Rates on Congenital Anomalies

Published rates of MCMs are available from the Centers for Disease Control and Prevention (CDC)'s Metropolitan Atlanta Congenital Defects Program (MACDP), which is an ongoing population-based birth defects surveillance program (Correa, 2007). The primary objectives of MACDP are to regularly and systematically monitor births of malformed infants for changes in incidence or other unusual patterns suggesting environmental influences, and to develop a case registry for use in epidemiological studies. MACDP actively searches for MCMs among the 50,000 annual births to residents of metropolitan Atlanta's 5 counties and abstracts medical records at all Atlanta obstetric hospitals, Atlanta pediatric referral hospitals, genetics labs, and vital records (Correa-Villasenor, 2003). While there are inherent problems with comparing data from women exposed to specific vaccines in pregnancy with background rates from the general population, this is not an unrealistic comparison (Honein, 1999), and background rates may be the only practical comparator. MACDP has been used as a comparator by over 60% of pregnancy registries identified in a recent survey (Covington, 2009). When an analysis includes data from an external comparator, it is important to thoroughly

understand the methodology of the external comparator, and to take this into consideration when designing the analysis plan ([Kennedy, 2004](#)).

Background Rates from Literature or Other Studies

The registry is committed to identifying other appropriate comparison groups, and research of the literature and other sources, such as other pregnancy registries or observational studies, will continue in order to obtain appropriate background rates.

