9.6.2 Software and Hardware

Power calculations presented in this protocol were conducted using SAS statistical software and a 1-sample binomial distribution with a 1-sided Type I error rate of 5%. Data analyses will be performed similarly using SAS (version 9.2 or higher; SAS Institute, Cary, NC).

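### Infants with MCMs are dropped from the registry's preterm and LBW rates but not, as stated, from the NVSS rates they are compared with, so both ratios lean slightly below 1

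*Protocol*

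**What the plan says.** Preterm birth and LBW are two of the three primary outcomes; MCM is the third. Section 9.7.3 gives both rates a denominator of live births and states: "These prevalence rates in exposed cases will be compared with those of the CDC NVSS". It then adds a restriction, on the ground that malformations tend to accompany both outcomes: affected infants are left out of "analyses of these outcomes and will not be counted in the numerator or denominator when prevalence rates are determined".

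Section 9.2.3.1 describes the comparator: "Background rates in the general population on pregnancy outcomes, such as premature birth and LBW, are readily available from national vital statistics". The only adjustment it describes for comparator rates is for age, as far as possible. Section 9.5 quotes the NVSS rates for mothers under 25 as 12.37% (preterm) and 8.70% (LBW), with no mention of malformations. Its preterm calculation reads: "With a sample size of approximately 58 exposed live births, the study will provide 80% power to detect a statistically significant 1.99-fold increase". The LBW figure is 2.40-fold, also on 58 live births.

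The abstract describes the same analysis without the exclusion: "The prevalence rates of preterm births and LBW will be calculated as proportions, with the number of live births as the denominator". This is an omission rather than a contradiction.

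**The concern.** The two sides of the comparison cover different sets of infants. The registry rate is for infants without an MCM, and the NVSS rate is for births in general. The protocol's reason for the exclusion is that infants with MCMs are more often preterm or of low birth weight. If so, removing them from one side only lowers that side, and the expected ratio is below 1 before any vaccine effect.

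There is also a structural problem. An MCM arises after exposure and is itself a primary outcome. Conditioning on its absence means that preterm birth or LBW accompanying a malformation cannot enter these two comparisons, however frequent it becomes.

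Both effects point towards missing harm, in a registry meant to detect safety signals. The protocol also departs from its own standard. Section 9.2.3.1 says it is important to "understand the methodology of the external comparator, and to take this into consideration when designing the analysis plan", and for MCMs the counting follows the convention of the comparator, the MACDP. For NVSS, the plan instead adds a restriction that the comparator is not said to have.

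**Working it through.** **Inputs from the protocol**
- NVSS rates p0: 12.37% preterm, 8.70% LBW (Section 9.5).
- Background MCM prevalence m = 2.54% (Section 9.5).
- 58 live births, 80% power, detectable folds 1.99 (preterm), 2.40 (LBW) and 4.46 (MCM) (Section 9.5).
- Test: "1-sample binomial distribution with a 1-sided Type I error rate of 5" per cent (Section 9.6.2).

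**Assumed input**
- RR, the risk of preterm birth or LBW in infants with an MCM relative to those without. Section 9.7.3 gives the direction but no size. I use 1 to 3, where 1 means no association.

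**Step 1: reproduce the plan's figures.** With an exact one-sided 5% binomial test at n = 58 against the unrestricted NVSS rates:

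| Outcome | Critical count | Actual alpha | Fold at 80% power | Stated |
|---|---|---|---|---|
| Preterm | 12 | 4.9% | 1.991 | 1.99 |
| LBW | 10 | 2.7% | 2.405 | 2.40 |

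The stated folds are right for all 58 live births. They do not describe the MCM-excluded set that Section 9.7.3 would analyse.

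**Step 2: how many infants are removed.** The expected number is 58 × 0.0254 = 1.47. The chance that none has an MCM is 0.9746^58 = 0.225.

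**Step 3: ratio under no vaccine effect.** Let q be the rate in infants without an MCM. The general rate is p0 = q(1 − m + m·RR), so the planned ratio is q/p0 = 1/(1 − m + m·RR).

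| RR | Planned ratio | Preterm rate (NVSS 12.37%) | LBW rate (NVSS 8.70%) |
|---|---|---|---|
| 1 | 1.000 | 12.37% | 8.70% |
| 2 | 1/1.0254 = 0.975 | 12.06% | 8.48% |
| 3 | 1/1.0508 = 0.952 | 11.77% | 8.28% |

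For RR 2 to 3 the shift is 0.3 to 0.6 points for preterm birth and 0.2 to 0.4 points for LBW. The standard error √[p0(1 − p0)/57] is 4.36 points for preterm and 3.73 points for LBW.

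**Step 4: a rise that comes through MCMs.** Let MCM prevalence rise k-fold with no other effect. The all-infant ratio is (1 − km + km·RR)/(1 − m + m·RR). The planned ratio does not contain k and so does not move. Take k = 4.46, the protocol's own detectable fold: km = 4.46 × 0.0254 = 11.33%, or about 6.6 of 58 infants.

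| RR | All-infant ratio | Preterm, all infants | LBW, all infants | Planned ratio |
|---|---|---|---|---|
| 2 | 1.1133/1.0254 = 1.086 | 13.4% | 9.4% | 0.975 |
| 3 | 1.2266/1.0508 = 1.167 | 14.4% | 10.2% | 0.952 |

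I give no power-loss figure, because part of any drop would come from the smaller n and the discreteness of the binomial test.

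**The case against.** The strongest reply is that this hardly matters. About 1.5 infants are affected, the shift is well inside sampling error, and its size rests on a relative risk that the protocol does not supply. In the 4.46-fold scenario, the separate MCM analysis has 80% power. An all-infant comparison would rarely flag the extra preterm births or LBW: with critical counts 12 and 10 at n = 58, the chance is 8 to 12% for preterm (4.9% with no effect) and 4 to 7% for LBW (2.7% with no effect). All of this stands. It limits the importance of the point, but it does not make the comparison like for like.

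A second reply is that the exclusion is deliberate: it isolates preterm birth and LBW not explained by malformation. That is a legitimate quantity, but it needs a comparator defined the same way, and none is named.

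Third, the excluded infants are not lost. MCM, preterm birth and LBW are each solicited as serious adverse events (Section 11.0), and the annual updates list preterm delivery and anomalies (Section 12.2). This is true, but those listings give no comparison with NVSS.

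Fourth, using all live births does not cure every mismatch. Pregnancies with an abnormal prenatal test before enrolment are left out of the primary analysis, so individually enrolled women may already have fewer MCMs than the general population, and 1.5 may be too high. In the other direction, the registry counts two or more conditional defects as an MCM (Section 9.3.2), which is broader than the MACDP definition behind the 2.54%. Neither point justifies a further one-sided exclusion.

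Finally, the SAP is not at hand and might restrict the comparator. However, the protocol itself fixes both the registry-side exclusion and the NVSS comparator, so this is a stated choice and not a detail left open.

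**Conclusion.** The concern holds. As written, the exclusion applies to the registry only, and the protocol's own reason for it implies ratios below 1 when there is no effect. At background MCM prevalence the bias is small: a ratio of 0.975 to 0.952 if RR is 2 to 3, and none if RR is 1. The inability to show a rise that comes through MCMs follows from the design and needs no assumed value; only its size does (all-infant 1.09 to 1.17 against planned 0.95 to 0.98 at a 4.46-fold MCM rise). The detectable folds in Section 9.5 are arithmetically correct but belong to a different analysis set. The plan should be changed, because the bias is systematic, affects two of the three primary comparisons, leans towards missing harm and is easily avoided.

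**What to change.** In Section 9.7.3, make the NVSS comparison of preterm birth and LBW on all live births, which is the set behind the Section 9.5 figures. Report the MCM-excluded rates next to it as a sensitivity analysis, with a note that the published NVSS rates are not a like-for-like comparator for them. Align the abstract, Section 9.5 and Section 9.7.3 so that all three describe the same denominator, and carry the wording into the SAP.

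The cost is a wording change and one extra tabulation from data already collected. No information is given up, since the MCM-excluded rates are still reported.
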